10.6.4. Clinical Laboratory Assessments

Details regarding clinical laboratory sample collection, preparation, and shipment are provided in the laboratory manual by the central laboratory. All laboratory assessments required by the protocol will be performed by a central laboratory unless otherwise stated or warranted due to special circumstances (eg, inability to ship to central laboratory due to COVID-19 restrictions, [Appendix 11](#)). Refer to [Table 3](#) for the list of clinical laboratory tests to be performed.

Clinical safety laboratory tests should be completed predose. The Investigator must review the laboratory report, document the review, and record any clinically relevant changes in the AE section of the eCRF (results of the white blood cell differential including ALC will be reviewed and monitored as described in Section [10.6.7.2](#)). The laboratory reports must be filed with the source documents.

All laboratory tests with values considered clinically significantly abnormal (ie, those that are AEs) during participation in the study or within 30 days after the last dose of study treatment should be repeated until the values return to normal range, have stabilized, or are no longer considered clinically significant by the Investigator. If such values do not return to normal or stabilized, or otherwise resolve to a non-clinically significant value within a reasonable period of time, as judged by the Investigator, the etiology should be identified, and the Medical Monitor should be notified. In cases when laboratory values from non-protocol-specified assessments are performed at the institution's local laboratory and result in a change in subject management or are considered clinically significant by the Investigator (eg, AE), then the results must be recorded in the eCRF.

Information on the grading and management of laboratory abnormalities according to assessed severity is provided in [Appendix 8](#) and [Appendix 9](#). See [Appendix 12](#) for suggested actions and follow-up assessments in the event of potential DILI.

Table 3: Clinical Laboratory Tests

Infectious Disease HIV-1 and -2 antibody, HBsAg, total anti-HBc, HCV antibody (if positive, reflex to HCV RNA quantification)
	
Coagulation International normalized ratio (INR) Activated partial thromboplastin time


Pregnancy and Postmenopausal Status Testing Serum pregnancy test for β-hCG (Screening or if positive urine pregnancy test; WOCBP only) Urine pregnancy test for β-hCG (Day 1 and monthly post-Day 1; WOCBP only) FSH (Screening; postmenopausal women only)
	

CBC with Differentials Hematocrit Hemoglobin Mean corpuscular hemoglobin Mean corpuscular hemoglobin concentration Mean corpuscular volume Platelet count Red blood cell count WBC^a count WBC differential count (absolute and %): lymphocytes, neutrophils, eosinophils, monocytes, basophils
	

TBNK Panel^a T, B, NK, CD4+ T cell and CD8+ T cell count (absolute number and percentage)
	

Serum Chemistry Albumin Alkaline phosphatase Alanine aminotransferase Aspartate aminotransferase Bicarbonate Blood urea nitrogen Calcium Chloride Creatinine
	
Glucose Potassium Sodium Total bilirubin Total protein

CCI
	

^a WBC count, WBC differential count, and TBNK panel will be assessed by an independent Medical Monitor during treatment (ie, after Day 1) until completion of the Double Blind Treatment Period dose selection analysis at Week 24 or subject discontinues study treatment (whichever occurs first) while the Investigators will assess the results of these lab parameters during Screening, on Day 1, and during the post treatment follow-up (refer to Section 10.6.7.2).

β -hCG, beta-human chorionic gonadotropin; CBC, complete blood count; FSH, follicle-stimulating hormone; HBsAg, hepatitis B surface antigen; anti-HBc, hepatitis B core antibody; HCV, hepatitis C virus; HIV, human immunodeficiency virus; INR, international normalized ratio; TBNK, T, B, NK, CD4+ T cell, and CD8+ T cell count (absolute number and percentage); WBC, white blood cell; WOCBP, woman of child-bearing potential

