6.5. Blinding

The study design includes a Double-Blind Treatment Period with limited access to the randomization code. The etrasimod and placebo tablets and bottles are identical in physical appearance. The treatment each subject receives will not be disclosed to the Investigator, study site staff, subject, Sponsor personnel involved with the conduct of the study (with the exception of the clinical supply staff and designated safety staff), or study vendors. The IWRS will hold treatment codes for study drug.

Site staff including investigators will be blinded to the following laboratory results while subject is on study treatment: WBC count, WBC differential (percentage and absolute number), and TBNK panel (T, B, NK, CD4+ T cell, and CD8+ T cell count [absolute number and percentage]). The monitoring of WBC count, WBC differential, and TBNK panel during the study are described in Section 10.6.7.2. Additionally, post-baseline esophageal histologic outcomes including eosinophil counts and Eosinophilic Esophagitis Histology Scoring System (EoE-HSS) scores will be blinded to site staff until the end of the study.

Treatment assignments in the Double-Blind Treatment Period and Extension Treatment Period should remain blinded for Sponsor, site staff, and subjects until the Week 24 dose selection analysis, unless that knowledge is necessary to determine a subject's emergency medical care. At the time of the 24-week Double-Blind Treatment Period analysis, the sponsor staff will be unblinded to the initial treatment assignments, but subjects, investigators and site staff will remain blinded. During the Extension Treatment Period, subjects, investigators, and site staff will be

aware that active treatment is being provided; however, they will remain blinded to the dose assignments.

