10.6.7. Safety Monitoring Guidance

10.6.7.1. Drug-Induced Liver Injury

There is no published consensus on exactly when to stop a drug in the face of laboratory abnormalities and the decision may be affected by the clinical status of the patient and many other factors. The following can be considered a basic guide. When there is no alternative etiology for persistently elevated liver enzymes, discontinuation of study treatment should be considered, consistent with the United States FDA guidance [49], if:

- ALT or AST $> 8 \times$ ULN
- ALT or AST $> 5 \times$ ULN for more than 2 weeks
- ALT or AST $> 3 \times$ ULN **and** (total bilirubin $> 2 \times$ ULN **or** INR > 1.5)
- ALT or AST $> 3 \times$ ULN with the appearance of fatigue, nausea, vomiting, right upper quadrant pain or tenderness, fever, rash, and/or eosinophilia ($> 5\%$)

See [Appendix 12](#) for suggested actions and follow-up assessments in the event of potential DILI. Information on the grading and management of laboratory abnormalities according to assessed severity is provided in [Appendix 8](#) and [Appendix 9](#).

10.6.7.2. Guidance on Management of Lymphocyte, Neutrophil, and White Blood Cell Counts, and Monitoring for Infections

Etrasimod prevents lymphocyte egress from lymphoid tissues, resulting in a reduction in peripheral lymphocyte count and lymphocyte availability for recruitment to sites of inflammation. Site staff including investigators will be blinded to the WBC count, WBC differential (percentage and absolute number), and the TBNK panel cell count while subjects are on study treatment. During this time, WBC count, WBC differential, and the TBNK panel results will be assessed by an independent Medical Monitor (not involved in any other aspects of study conduct or data analysis) and will direct Investigators on specific actions to take. Blinded values may be released to treating physicians and Investigators as deemed medically necessary to monitor the risk of infection and/or aid in diagnostic work-up as clinically indicated, and/or as a tool to assess the effectiveness of therapeutic interventions for an infection.

ALC

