The independent Medical Monitor will notify Investigators when the subject has an absolute lymphocyte count (ALC) $< 0.2 \times 10^9$ cells/L. In this scenario, the Investigator will be asked to have the subject return for a repeat CBC with differential within 7 days to confirm the ALC. If the ALC is confirmed to be below 0.2×10^9 cells/L, study treatment should be interrupted. While study treatment is interrupted, the Investigator will repeat the CBC with differentials weekly until ALC is $> 0.5 \times 10^9$ cells/L. Re-initiation of the study treatment can be considered when ALC is $> 0.5 \times 10^9$ cells/L. ALC recovery is expected to occur within 7 to 10 days after study treatment interruption.

When there is a sustained decreased in ALC $< 0.2 \times 10^9$ cells/L, defined as having a second confirmed ALC $< 0.2 \times 10^9$ cells/L with treatment rechallenge (after the initial study treatment interruption due to a low ALC), study treatment must be permanently discontinued.

Subjects with an ongoing AE of decreased lymphocyte count or infection at the post-treatment 4 Week Follow-Up Visit will continue to have weekly CBC with differential until ALC recovery is achieved (defined as ALC return to within the normal range or to at least 80% of the pre-treatment value).

ANC and WBC

In addition, the independent Medical Monitor will notify Investigators when there is at least 1 measurement of ANC $< 1.0 \times 10^9$ cells/L or WBC count $> 20 \times 10^9$ cells/L.

Investigators will repeat the CBC with differentials weekly until ANC $> 1.0 \times 10^9$ cells/L or the increased WBC count trends downward (on 2 separate days), respectively.

Refer to Section 10.6.7.3 for information on monitoring for signs and symptoms of infections and diagnostic work-up and treatment of infections.

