4.1. MAIN ANALYSIS

A Main Analysis will take place for this study at the end of the Double-Blind Treatment Period when all subjects have completed Week 24 visit or discontinued from the study prior to Week 24. The results of which will be based on the unblinded treatment groups. All planned Main Study Analyses identified in this SAP will be performed by IQVIA Biostatistics following Pfizer Pharmaceutical Sponsor Authorization of this SAP, database unblinding, and Analysis Sets.

Derivations and definitions for the Main Analysis will be based on those required for the final analysis contained in this SAP, unless deviations are stated within the text. The list of outputs provided with the full set of output templates (planned for the final analysis) will highlight which of these outputs will also be provided for the Main Analysis.

After all subjects have completed the Double-Blind Treatment Period or discontinued from the study prior to Week 24, outstanding data queries have been resolved/closed, and the data have been cleaned and finalized, the sponsor will authorize breaking of the study blind for Double Blind Treatment Period and the Main Analysis of the data will be performed. No treatment assignment unblinded, or analyses completed until this SAP has been approved.

At the time of the main analysis, the sponsor staff will be unblinded to the initial treatment assignments at the beginning of Double-Blind Treatment Period, but participants, investigators and site staff will remain blinded. During the Extension Treatment Period, participants, investigators, and site staff will be aware that active treatment is being provided; however, they will remain blinded to the dose assignments. An unblinded team at IQVIA will receive the Double-Blind Treatment assignments and perform the Main Analysis

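### Protocol Table 3 footnote a ends the independent Medical Monitor's review of blood counts at the Week 24 analysis, contradicting Section 10.6.7.2, which assigns that review for all time on treatment

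*Protocol*

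**What the plan says.** Three parts of the protocol give the same rule.

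- Section 6.5: "Site staff including investigators will be blinded to the following laboratory results while subject is on study treatment". The results listed are WBC count, WBC differential and the TBNK panel.
- Section 10.6.7.2 repeats that blinding for time on study treatment and continues: "During this time, WBC count, WBC differential, and the TBNK panel results will be assessed by an independent Medical Monitor". It sets no end at Week 24.
- The body text of Section 10.6.4 defers to that section: "results of the white blood cell differential including ALC will be reviewed and monitored as described in Section" 10.6.7.2.

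Table 3 footnote a in Section 10.6.4 covers the same three tests but gives a different period. The Monitor's assessment starts once Day 1 is past and lasts "until completion of the Double Blind Treatment Period dose selection analysis at Week 24 or subject discontinues study treatment", with the earlier of these two events ending it. Investigators have the results at other times only, namely at Screening, on Day 1 and in the follow-up after treatment. The footnote then refers the reader to 10.6.7.2.

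Study treatment does not end at Week 24. Section 3.1 provides 28 weeks of active extension treatment, and Table 8 schedules laboratory tests (including CBC with differential) and TBNK at Weeks 28, 32, 46 and 52.

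**The concern.** The footnote closes the Monitor's review while subjects may still be taking etrasimod, and it passes the task to no one. Investigators receive the results again only after treatment, and Sections 6.5 and 10.6.7.2 keep them blinded until then.

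The count-based safety actions in 10.6.7.2 start with the Monitor:

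- For lymphocytes, the Monitor's notice of ALC below 0.2 × 10^9/L prompts a repeat CBC within 7 days. A confirmed low value leads to interruption and weekly CBCs until ALC exceeds 0.5 × 10^9/L.
- For neutrophils, "the independent Medical Monitor will notify Investigators when there is at least 1 measurement of ANC" below 1.0 × 10^9/L. A WBC count above 20 × 10^9/L is handled the same way.
- Section 8.1 makes discontinuation mandatory for a second confirmed low ALC on rechallenge. That cannot arise if the first low value is never flagged.

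Section 1.2 expects a dose-dependent fall in lymphocytes and names serial WBC and differential assessment as the means of judging infection risk. Subjects re-randomized from placebo first receive etrasimod in the extension, so all their on-drug counts fall in the period where the two rules can conflict.

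**Working it through.** **Text comparison.** The documents give no figure for this, so the first step is to see who reviews the counts in each period.

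| Period | Sections 6.5 and 10.6.7.2 | Table 3 footnote a |
|---|---|---|
| Screening, Day 1 | Not restricted (before or at start of treatment) | Investigators |
| On treatment, until the Week 24 analysis is completed | Monitor; sites blinded | Monitor |
| On extension treatment, after that analysis is completed | Monitor; sites blinded | No one named |
| Post-treatment follow-up | Site blinding has ended | Investigators |

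The conflict is confined to the third row.

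**How long that row lasts.** The cut-off is completion of a study-level analysis, not each subject's own Week 24 visit. SAP Section 4.1 places that analysis "when all subjects have completed Week 24 visit or discontinued from the study prior to Week 24", and it also requires queries to be closed and data cleaned first.

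Inputs:

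- Extension length: 28 weeks (Protocol 3.1).
- Extension count visits: Weeks 28, 32, 46 and 52 (Table 8), which are 4, 8, 22 and 28 weeks after Week 24.
- L: weeks from the last subject's Week 24 visit to completion of the analysis. Not in the documents; assumed.
- a: weeks by which a given subject reached Week 24 before that last subject. Not in the documents; assumed.

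Formulas:

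- Treatment weeks after the cut-off = max(0, 28 − L − a).
- Visits after the cut-off = how many of 4, 8, 22 and 28 exceed L + a.

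The last column leaves out Week 52. Table 8 dispenses no drug at that visit, so a count drawn then has no further scheduled treatment to interrupt.

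| a | L | Weeks after cut-off | Count visits after cut-off | Of these, before Week 52 |
|---|---|---|---|---|
| 0 | 4 | 28 − 4 = 24 | 3 (Weeks 32, 46, 52) | 2 |
| 0 | 12 | 28 − 12 = 16 | 2 (Weeks 46, 52) | 1 |
| 0 | 20 | 28 − 20 = 8 | 2 (Weeks 46, 52) | 1 |
| 0 | 24 | 28 − 24 = 4 | 1 (Week 52) | 0 |
| 0 | 28 or more | 0 | 0 | 0 |
| 20 | 4 | 28 − 24 = 4 | 1 (Week 52) | 0 |
| 20 | 8 or more | 0 | 0 | 0 |

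Affected treatment time reaches zero when L + a is 28 weeks or more. Visits at which an interruption could still follow run out sooner, when L + a is 22 weeks or more.

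**The case against.** The best defence is that the operative rule is clear and the footnote is a stray. Sections 6.5, 10.6.7.2 and 8.1 and the body of 10.6.4 are consistent, none has a Week 24 limit, and the footnote itself sends the reader to 10.6.7.2. A team that follows the section has no gap. The claim that no one reviews the counts also combines two texts: the footnote's stop and the site blinding stated elsewhere. Sponsor staff are unblinded to the initial assignments at that same analysis, so a hand-over may have been intended. Finally, the exposure is assumed and may be zero, Week 52 gives no chance to interrupt, and some safeguards remain.

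Several of these points stand. Harm arises only if the footnote is followed, and the size is conditional. The Week 52 point is right as far as interruption goes. Release of blinded values when medically necessary (10.6.7.2) and vigilance for infection (10.6.7.3) still apply.

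They do not remove the problem. The footnote states an explicit stop, and a cross-reference does not cancel it. No section assigns these counts to sponsor staff or anyone else after the analysis. The remaining safeguards respond to events and do not replace routine review of a laboratory finding that may have no symptoms.

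**Conclusion.** The concern holds: footnote a is wrong as written and should be fixed. The contradiction is certain from the text. Its practical effect is conditional. It arises only if staff follow the footnote rather than 10.6.7.2, and only for subjects still on extension treatment when the Week 24 analysis is completed.

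Over the assumed values of L, the last subject would have between 24 weeks with 3 count visits and no affected time; subjects ahead of the last have less. The number of subjects affected cannot be derived, because the documents give neither accrual timing nor the time the analysis takes.

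**What to change.** In Table 3 footnote a, delete the clause that ends review at completion of the Week 24 analysis, together with the whichever-occurs-first qualifier. State that the Monitor assesses these results after Day 1, including the Extension Treatment Period, until the subject stops study treatment. Leave the Investigators' periods (Screening, Day 1, post-treatment follow-up) as they are.

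This aligns the footnote with Sections 6.5 and 10.6.7.2. Sites stay blinded to the counts during the extension, and no threshold or action changes. If the sponsor did intend a different reviewer after the analysis, 6.5 and 10.6.7.2 must be amended to name that reviewer.

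The recommended edit costs one footnote change, by amendment or clarification letter. The Monitor role and procedures already exist in 10.6.7.2.

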10.6.5. Pulmonary Function Test

PFTs will be performed according to the Schedules of Assessments ([Appendix 1](#); [Table 7](#) and [Table 8](#)). Where locally available, diffusing capacity of the lungs for carbon monoxide (DLCO) measurements will also be performed (sites where DLCO is not available should consult the Sponsor or Sponsor's delegate). Because carbon monoxide binds readily to hemoglobin, the diffusion capacity needs to be corrected for hemoglobin in order to reflect an altered lung gas transport rather than altered hemoglobin. All DLCO values will be corrected for hemoglobin concentration (ie, hemoglobin-adjusted diffusion capacity) in the study.

PFTs and DLCO (or other acceptable pulmonary function methods) will be conducted in all subjects in a manner consistent with the American Thoracic Society/European Respiratory Society guidelines for standardization of spirometry and single breath determination of carbon monoxide uptake in the lung [55-57]. Concern has been raised that pulmonary function testing could represent a potential avenue for COVID-19 transmission due to the congregation of patients with lung disease and because of the potential for coughing and droplet formation surrounding pulmonary function testing procedures. Refer to [Appendix 11](#) for modifications in the event that COVID-19 or similar PHE-related restrictions limit the capacity to perform non-essential PFTs.

Patient respiratory history will be collected at the Screening Visit, and any condition that might affect the outcome of PFT, including infection, respiratory symptoms, occupational exposures (including asbestos) and cigarette smoking, will be collected before every PFT and recorded in the eCRF. Furthermore, any issues with patient effort or compliance with the test procedure should be explicitly recorded in the eCRF. This information is important to determine whether PFT abnormalities may be the result of poor effort or compliance with test procedure. Smoking status (including ecigarettes) will be collected and recorded in the eCRF each time a PFT assessment is conducted.

Subjects reporting any respiratory symptoms (eg, dyspnea, shortness of breath, chest tightness, or wheezing) should be seen at an unscheduled visit for clinical assessment and full PFT assessment, preferably on the same day.

Additional guidance on clinical monitoring of pulmonary function is provided in [Section 10.6.7.5](#).

10.6.6. Ophthalmoscopy and Optical Coherence Tomography

A complete ophthalmoscopy and OCT assessment will be performed according to the Schedules of Assessments ([Appendix 1](#); [Table 7](#) and [Table 8](#)) and all ophthalmic findings should be recorded in eCRF.

The OCT machine used should preferably not be changed during the study to allow for comparison of central foveal thickness measurements within each subject across timepoints.

The ophthalmologist should be provided with a study referral letter explaining the reason for the referral along with information about the study, the investigational drug, and the ophthalmic clinical data to be collected for the study.

At the Screening and Post-Screening Visits, eye examination performed by an ophthalmologist will include:

- Ophthalmologic history
- Best corrected visual acuity measurement (autorefraction, using Snellen chart internationally)
- Ophthalmoscopy
 - May include contact lens biomicroscopy to examine the macula and optic disc
 - A dilated fundus exam should be performed in all subjects at the Screening Visit and as needed at subsequent visits in subjects with significant abnormalities identified on the screening exam. Subjects should be advised to wear sunglasses after pupil dilation and arrange for a driver to transport them after the exam
- Retinal photographs (only if evidence of clinically significant abnormalities)
- OCT for the measurement of central foveal thickness (recorded in micrometers)
- Fluorescein angiogram (FA) (at the discretion of the ophthalmologist) if there is a suspicion of macular edema by ophthalmoscopy and increased central foveal thickness by OCT

Subjects experiencing unexpected ophthalmic symptoms without a known suspected etiology or experiencing a relevant ophthalmic AE may need to have repeat ophthalmoscopy and OCT testing performed.

Additional guidance on clinical monitoring of ophthalmic symptoms is provided in Section 10.6.7.6.

10.6.7. Safety Monitoring Guidance

10.6.7.1. Drug-Induced Liver Injury

There is no published consensus on exactly when to stop a drug in the face of laboratory abnormalities and the decision may be affected by the clinical status of the patient and many other factors. The following can be considered a basic guide. When there is no alternative etiology for persistently elevated liver enzymes, discontinuation of study treatment should be considered, consistent with the United States FDA guidance [49], if:

- ALT or AST $> 8 \times$ ULN
- ALT or AST $> 5 \times$ ULN for more than 2 weeks
- ALT or AST $> 3 \times$ ULN **and** (total bilirubin $> 2 \times$ ULN **or** INR > 1.5)
- ALT or AST $> 3 \times$ ULN with the appearance of fatigue, nausea, vomiting, right upper quadrant pain or tenderness, fever, rash, and/or eosinophilia ($> 5\%$)

See [Appendix 12](#) for suggested actions and follow-up assessments in the event of potential DILI. Information on the grading and management of laboratory abnormalities according to assessed severity is provided in [Appendix 8](#) and [Appendix 9](#).

10.6.7.2. Guidance on Management of Lymphocyte, Neutrophil, and White Blood Cell Counts, and Monitoring for Infections

Etrasimod prevents lymphocyte egress from lymphoid tissues, resulting in a reduction in peripheral lymphocyte count and lymphocyte availability for recruitment to sites of inflammation. Site staff including investigators will be blinded to the WBC count, WBC differential (percentage and absolute number), and the TBNK panel cell count while subjects are on study treatment. During this time, WBC count, WBC differential, and the TBNK panel results will be assessed by an independent Medical Monitor (not involved in any other aspects of study conduct or data analysis) and will direct Investigators on specific actions to take. Blinded values may be released to treating physicians and Investigators as deemed medically necessary to monitor the risk of infection and/or aid in diagnostic work-up as clinically indicated, and/or as a tool to assess the effectiveness of therapeutic interventions for an infection.

ALC

The independent Medical Monitor will notify Investigators when the subject has an absolute lymphocyte count (ALC) $< 0.2 \times 10^9$ cells/L. In this scenario, the Investigator will be asked to have the subject return for a repeat CBC with differential within 7 days to confirm the ALC. If the ALC is confirmed to be below 0.2×10^9 cells/L, study treatment should be interrupted. While study treatment is interrupted, the Investigator will repeat the CBC with differentials weekly until ALC is $> 0.5 \times 10^9$ cells/L. Re-initiation of the study treatment can be considered when ALC is $> 0.5 \times 10^9$ cells/L. ALC recovery is expected to occur within 7 to 10 days after study treatment interruption.

When there is a sustained decreased in ALC $< 0.2 \times 10^9$ cells/L, defined as having a second confirmed ALC $< 0.2 \times 10^9$ cells/L with treatment rechallenge (after the initial study treatment interruption due to a low ALC), study treatment must be permanently discontinued.

Subjects with an ongoing AE of decreased lymphocyte count or infection at the post-treatment 4 Week Follow-Up Visit will continue to have weekly CBC with differential until ALC recovery is achieved (defined as ALC return to within the normal range or to at least 80% of the pre-treatment value).

ANC and WBC

In addition, the independent Medical Monitor will notify Investigators when there is at least 1 measurement of ANC $< 1.0 \times 10^9$ cells/L or WBC count $> 20 \times 10^9$ cells/L.

Investigators will repeat the CBC with differentials weekly until ANC $> 1.0 \times 10^9$ cells/L or the increased WBC count trends downward (on 2 separate days), respectively.

Refer to Section 10.6.7.3 for information on monitoring for signs and symptoms of infections and diagnostic work-up and treatment of infections.

